## TR-based assessments

Several behavioral assessments will be completed remotely during Weeks 1 to 6 using the TR system. These will be scored during supervised sessions, while the therapist is in the videoconference. In addition, once each week, the therapist will ask the patient about interval medical history and AEs.

### Daily assessments performed using the TR system

- Daily motor assessment (Whack-A-Mole game using the hand, scores # targets hit in 90 seconds)
- Daily finger tap assessment (scores # index finger taps on small button in 10 sec, reported in Hz)
- Daily shoulder pain scoring— uses Visual Analog Scale (VAS)
- Daily fatigue scoring— uses VAS
- Degree of Perceived Effort – uses VAS

### Week 1 additional assessments

- EuroQoL Visual Analog Scale (EQ VAS)
- Stroke Education Quiz (5 questions/day x 6 days)
- The patient will be asked about interval medical history and AEs

### Week 2 additional assessments

- Stroke impact scale – ADL and Hand subsections (administered during week 2 or within 5 days of DC home)
- General Anxiety Disorder 7-item (GAD-7) Scale
- Screening question for possible diagnosis of Restless Legs Syndrome
- The patient will be asked about interval medical history and AEs

### Week 3 additional assessments

- Reaction Time Test
- Medical Outcomes Study Social Support Survey (MOS-SSS)
- Center for Epidemiologic Studies Short Depression Scale (CESD-R-10)
- OPS and PACES
- Guess Medication (Patients asked which pill they think they were taking each day.)
- The patient will be asked about interval medical history and AEs

### Week 4 additional assessments

- Brief Resilience Scale (BRS)
- The patient will be asked about interval medical history and AEs

### Week 5 additional assessments

- The patient will be asked about interval medical history and AEs

### Week 6: additional assessments

- Stroke Education Quiz (5 questions/day x 6 days)
- Reaction Time Test
- EQ VAS
- CESD-R-10
- OPS and PACES

Dopaminergic enhancement of rehabilitation therapy early after stroke (TR-Dopa)  
Protocol\_20230721

- Patient Satisfaction with Telerehabilitation Survey
- The patient will be asked about interval medical history and AEs

## Visit 3 (End of Treatment)

The end-of-treatment visit will generally be conducted at Cal Rehab, but accommodations for home assessment will be made as needed.

If the testing occurs in the patient's home, two research staff members should be present, when possible: one person to conduct final assessments with the patient and the other to deconstruct and clean equipment for transport back to the lab.

## Assessments

*Several standardized assessments will be conducted during this in-person visit:*

- FMA-UE
- BBT
- ARAT
- NHPT
- mRS
- SIS-hand and ADL subsections
- In addition, the patient will be asked about interval medical history and AEs

## Deconstructing and cleaning equipment

A member of the research team will deconstruct, clean, and pack the TR system for transport back to the lab while the examiner is conducting assessments with the patient.

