## Randomize the patient

Using a web-based randomization procedure, the patient will be randomized into one of three treatment groups:

- **TR + Sinemet:** Patients in this group will receive 36 therapy sessions targeting arm motor function starting as soon as possible after randomization (target is next day). This therapy is structured as 6 weeks of TR, 6x/week, for 6 weeks. Up to 8 weeks are permitted to make up for lost sessions to achieve 36 sessions in which >50% of assigned minutes are completed by the patient. For the first 18 sessions (approximately the first 3 weeks), the patient will take their study pill (Sinemet 25/100) 1-2 hours after breakfast or lunch, then 1 hour later begin their 70-min TR session. TR+Sinemet is in addition to UC (i.e., the patient is to continue all therapies and medication provided as part of standard medical care).
- **TR + placebo:** Patients in this group will receive 36 therapy sessions targeting arm motor function starting as soon as possible after randomization (target is next day). This therapy is structured as 6 weeks of TR, 6x/week, for 6 weeks. Up to 8 weeks are

permitted to make up for lost sessions to achieve 36 sessions in which >50% of assigned minutes are completed by the patient. For the first 18 sessions (approximately the first 3 weeks), the patient will take their study pill (placebo) 1-2 hours after breakfast or lunch, then 1 hour later begin their 70-min TR session. TR+placebo is in addition to UC (i.e., the patient is to continue all therapies and medication provided as part of standard medical care).

- **Usual care (UC):** Patients in this group will not receive TR or a blister pack of study pills. Instead, each will receive UC (i.e., will continue all therapies and medication provided as part of standard medical care). In order to maximize participant retention, patients in this group will be offered a 6-week course of TR after Visit 4 (i.e., 5-6 months after stroke). At the end of their TR therapy, at the time that their TR system is picked up from their home, the therapist will perform ARAT, FMA-UE, BBT, NHPT, and mRS in the patient's home.

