## TR Therapy

### The telerehabilitation intervention

**Summary:** Patients are assigned 70 minutes of telerehabilitation (TR) therapy each day, 6 days/week, for 6 weeks, targeting the paretic UE. Functional games and exercises comprise 65 of these daily minutes, and 5 minutes/day is spent on stroke education (which requires targeted arm movement).

Therapy must begin within 7 days of randomization. The first TR session will be a supervised session, whether in-person or via videoconference.

TR is delivered over 36 sessions, each 70-minutes in duration. Of these, 18 sessions are supervised by a licensed OT or PT; for patients receiving TR while admitted to Cal Rehab, the therapist may be in the same room as the patient or communicate via videoconference, and for patients who are at home, the therapist is present via videoconference. The other 18 sessions are unsupervised (i.e., no OT or PT is present at any time during the session; for inpatients at Cal Rehab, the therapist can sit near the patient, with minimal interaction, at the therapist's judgment). Ideally, a given patient will work with the same therapist for the entire 6 weeks. To accommodate possible external events (e.g., illness or family reasons), patients are permitted up to 8 weeks to complete these 36 treatment sessions. In the prior national trial, the FDA determined (Q140628) that the investigation using an earlier generation of the same device was a non-significant risk device study. The FDA made the same determination (Q212693) for the current study. When possible, patients begin TR each day at the time indicated in the behavioral contract. Patients are free to pause between games and activities, as needed. Patients are also instructed to perform all UC that is provided to them—enrollment in this TR study does not interfere with any treatment provided as part of standard of care. A session is considered completed when the patient has completed >50% of the assigned 70 minutes by midnight. After the 36 treatment sessions are completed, or if that does not happen then at the end of 8 weeks, the team retrieves the TR system from the patient's home.

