### Blinding

With regard to TR vs. UC, study assessors will be blind to treatment assignment. Several steps will be taken to maintain this blind, including having assessments occur in a separate part of the building from TR therapy.

With regard to TR+Sinemet vs. TR+placebo, enrollees and their family members, study assessors, study treatment therapists, clinicians involved in UC, the study PI, and all other study personnel will remain blinded to type of pill assigned. The sole person unblinded to pill type (for patients randomized to either TR+Sinemet or TR+placebo) will be the study statistician. With regard to the pill to which a TR patient was assigned, the study PI will be able to break the blind at any time in case of a medical emergency requiring this knowledge. To enable this, a password-protected file and a hard copy sealed envelope will both be in the PI's possession and will remain unopened unless an emergency unblinding event arises.

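### At a home Visit 3 the TR system is packed up while the examiner scores the patient, which probably reveals the TR group and conflicts with the promised assessor blinding

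*Combined protocol and SAP*

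**What the plan says.** The Blinding section states: "With regard to TR vs. UC, study assessors will be blind to treatment assignment". It refers to several steps that protect this blind and names one of them, "having assessments occur in a separate part of the building from TR therapy".

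Under Visit 3 (End of Treatment), the visit "will generally be conducted at Cal Rehab, but accommodations for home assessment will be made as needed". For a home visit, "two research staff members should be present, when possible". The plan then divides the work between them: "one person to conduct final assessments with the patient and the other to deconstruct and clean equipment". The next section but one, Deconstructing and cleaning equipment, fixes the timing: a staff member "will deconstruct, clean, and pack the TR system for transport back to the lab while the examiner is conducting assessments with the patient".

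Two other places bear on this. The UC paragraph of Randomize the patient says "Patients in this group will not receive TR or a blister pack of study pills", and UC patients are offered TR only after Visit 4. The section on the telerehabilitation intervention says that once the 36 sessions are done, "or if that does not happen then at the end of 8 weeks, the team retrieves the TR system" from the home.

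**The concern.** For the TR versus UC comparison, assessor blinding is the only masking the plan describes; patients necessarily know whether they are using a TR system. A home Visit 3 run as written puts the examiner in the same home, at the same time, as the dismantling of a computer, table, chair and set of input devices that only TR patients have. If the examiner sees this, or only notices why the colleague came, the group is known before or during scoring.

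Any resulting rating bias would not be balanced between groups, because the cue arises in TR homes. It would bear most on outcomes that need the rater's judgement: ARAT, FMA-UE and mRS. ARAT change to Visit 3 is a named secondary analysis. FMA-UE, BBT, mRS and SIS-hand at Visit 3 are corollary analyses, and Visit 3 mRS also enters the shift analysis. BBT is a count and less exposed.

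**Working it through.** **1. The texts side by side**

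| Question | What the plan provides |
|---|---|
| Should the Visit 3 examiner know TR versus UC? | No (Blinding) |
| Can Visit 3 be at home? | Yes, as an exception (Visit 3) |
| Where is the TR system then? | In the home, being packed during the assessment (Deconstructing and cleaning equipment) |
| Could a UC home have one at that time? | No; UC patients are offered TR only after Visit 4 (Randomize the patient) |
| Does the named blinding step cover a home? | No; it concerns parts of one building (Blinding) |
| Is another safeguard for home visits described? | None in these documents: no separate room, no prior removal, no record of the examiner's guess. The Week 3 medication guess asks patients about their pill only |

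The cue identifies TR, and nothing in the text keeps it from the examiner. The text does not say that the packing is in view, so unblinding is likely rather than certain.

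**2. The plan's own sample size, to fix the scale**

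Inputs from Sample Size: 54 TR (27 + 27), 18 UC, SD 7.4, difference 5.7, two-sided alpha 0.05.

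- SE = 7.4 × √(1/54 + 1/18) = 2.014
- Power at 5.7 points = 80.8% (normal approximation) or 79.7% (non-central t, 70 df), so the stated 80% with 72 patients is reproduced.

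**3. Illustration for Visit 3 ARAT**

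The plan gives neither the share of home visits nor any size for rater bias. Assume that k of the 54 TR patients are rated at home by an unblinded examiner and that each is scored b points too high. The shift in the TR minus UC difference is (k/54) × b. Type I error is the two-sided rejection probability of a non-central t with 70 df and non-centrality shift/SE.

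| k (share of TR) | b | Shift | Shift/SE | Type I error |
|---|---|---|---|---|
| 5 (9%) | 1 | 0.093 | 4.6% | 0.0502 |
| 5 (9%) | 3 | 0.278 | 13.8% | 0.0521 |
| 13 (24%) | 1 | 0.241 | 12.0% | 0.0516 |
| 13 (24%) | 3 | 0.722 | 35.9% | 0.0645 (0.06445 before rounding) |
| 27 (50%) | 3 | 1.500 | 74.5% | 0.1137 |

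The first four rows treat home visits as the exception, as the plan does. The last row shows what would happen if they became common.

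**4. Primary endpoint**

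Visit 4 is one month after Visit 3, and the system should have been collected by then. Bias there requires that the same examiner rates the patient again and is influenced by what was learned. The plan gives no rule for assigning raters at Visit 4, so this can be neither assumed nor excluded, and no figure is offered.

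**The case against.** The strongest case against is about weight, not about the conflict itself. Visit 3 is normally at Cal Rehab, its analyses are secondary or corollary, the primary endpoint comes a month later, and the comparison of Sinemet with placebo is untouched because both of those arms have the system. All of this stands, and it limits the concern.

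The numbers also deserve caution. The home-visit share and the bias are assumed, and the upper end of the range follows directly from those choices. The SE is for an unweighted comparison on the raw scale, whereas the plan calls for an inverse-propensity-weighted t test on the log scale and also an ANCOVA. The sample-size SD is borrowed for change to Visit 3. The sketch leaves out UC patients, whose homes show no system and might be recognised for that reason; each is 1 of 18, or 5.6% of that group. The figures therefore indicate an order of magnitude and are not an estimate for the planned analysis.

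Two points of reading are fair. The list of blinding steps is worded as incomplete, and operational detail may sit in forms or procedures outside these documents. That a lone examiner might be in the home with the system is an inference from the staffing being required only where possible; the equipment section itself assumes two people.

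Finally, patients can disclose their group at any visit, in clinic or at home. That risk exists anyway. The packing adds a cue that the plan itself creates and can easily remove, so the objection does not defeat the point.

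**Conclusion.** The concern holds. The Visit 3 home procedure and the Blinding section cannot both be followed with confidence: carried out as written, the procedure would probably unblind the examiner to TR versus UC, and the cue arises only in TR homes.

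The exposure is to the Visit 3 comparisons of TR with UC. With 9% to 24% of TR patients affected and 1 to 3 points of over-scoring, all assumed, the ARAT difference moves by 0.09 to 0.72 points, or 5% to 36% of its standard error, and type I error lies between 0.050 and 0.064. The effect is small unless home visits are common. For the primary Visit 4 ARAT the risk is conditional on examiner overlap and carry-over and cannot be sized. Aim 2 is not affected. The passages should be reconciled, because the contradiction is clear and the repair costs little.

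**What to change.** Revise the home-visit text under Visit 3 and the section on deconstructing equipment. Staff other than the examiner should retrieve the TR system before the examiner arrives or on a separate trip, never during the assessment. Ask patients not to mention the system to the examiner. Because the plan already has the team collect the system once the 36 sessions or 8 weeks are over, pick-up can come first without loss of therapy. With the system gone beforehand, its absence from a UC home also stops being informative.

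The cost is two rewritten sentences and an extra or rescheduled trip, within the 30 miles set by exclusion criterion 15, for the TR patients who are assessed at home.

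Optionally, record the examiner's guess of TR versus UC at Visits 3 and 4. This adds one form item and would show whether the blind held, including against disclosure by patients.

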## Visit 4 (End of Study)

The end-of-study visit will generally be conducted at Cal Rehab, but accommodations for home assessment will be made as needed; this visit occurs 1 month after Visit 3. Visit 4 may be broken into more than one session, as needed. All Visit 4 assessments are available in a single “Visit 4” packet, located in the lab’s Box folder. Details regarding administration of each assessment is found within individual CRFs.

### Assessments

The following assessments will be completed during this final in-person visit:

- ARAT
- BBT
- mRS
- FMA-UE
- NHPT
- SIS—ADL and hand subsections
- The patient will be asked about interval medical history and AEs

## Visit 5 (for UC only)

As previously mentioned, patients in the UC group will be offered a 6-week course of TR after Visit 4 (i.e., 5-6 months after stroke). For those subjects who choose to complete this training, the same assessments administered at Visit 4 will be re-assessed at Visit 5. These include the following:

- ARAT
- BBT
- mRS
- FMA-UE
- NHPT
- SIS—ADL and hand subsections
- The patient will be asked about interval medical history and AEs

## Randomization and Blinding

### Randomization

A web-based randomization procedure will be used to assign patients to one of three groups in a 3:3:2 ratio. The three treatment groups are [1] TR plus Sinemet, [2] TR plus placebo, and [3] UC.

### Blinding

With regard to TR vs. UC, study assessors will be blind to treatment assignment. Several steps will be taken to maintain this blind, including having assessments occur in a separate part of the building from TR therapy.

With regard to TR+Sinemet vs. TR+placebo, enrollees and their family members, study assessors, study treatment therapists, clinicians involved in UC, the study PI, and all other study personnel will remain blinded to type of pill assigned. The sole person unblinded to pill type (for patients randomized to either TR+Sinemet or TR+placebo) will be the study statistician. With regard to the pill to which a TR patient was assigned, the study PI will be able to break the blind at any time in case of a medical emergency requiring this knowledge. To enable this, a password-protected file and a hard copy sealed envelope will both be in the PI's possession and will remain unopened unless an emergency unblinding event arises.

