## Dispense Study Medication

Study medication will be dispensed at Visit 1, or shortly after. Patients randomized to the TR+Sinemet and the TR+placebo groups will be given a blister pack of 18 pills with instructions to take one pill an hour after breakfast or lunch 6 days/week for the first 18 sessions (approximately the first 3 weeks). TR will begin 1 hour after pill ingestion. Patients will be given apple sauce to take with their pill as needed, following dysphagia restriction guidelines, to mitigate concerns for potential nausea. As needed, patients may also be provided with an antacid drug. Patients in the UC group will not be given a blister pack of study pills or apple sauce.

The UCLA Pharmacy will generate the two types of study pills (i.e., Sinemet 25/100 and placebo). These two pills will be indistinguishable internally and externally (i.e., the internal powder will be the same color, and the external over-encapsulation will be identical), across both pill types. Pills will be organized into an 18-pill blister pack.

In patients with stroke, oral Sinemet 25/100 once/day is not associated with increased risk or with decreased acceptability of risks For this reason, the current study does not need to be conducted under an investigational new drug application to the FDA.

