### Statistical Analysis

We will present descriptive statistics by group for the important covariates including age, site, time from stroke to randomization, MEP status, and hours of outside rehabilitation. We will also report compliance, defined as the percentage of the 36 sessions during which patients complete more than half ( $\geq 36$  min) of assigned activities. For all analyses, data not normally distributed will be appropriately transformed.

Primary efficacy analysis will use the Intent-To-Treat population, consisting of all randomized subjects and multiple imputation for missing data. Secondary analysis will examine the Per-Protocol population, defined as all subjects with complete data who complete  $\geq 36$  minutes of assigned activities on  $\geq 30$  of the 36 therapy sessions over no more than 8 weeks. Analyses will be performed using SAS and R software.

Logistic regression will be used to create a propensity score for treatment group using age, time from stroke to randomization, and total hours of outside rehabilitation therapy from Visit 1 to Visit 4 (or Visit 3 when change is to visit 3). Inverse weights based on this score will be used in secondary analyses to compute adjusted change distributions and corresponding p values. The primary analyses will be based on the inverse propensity score weighted (adjusted) change from base. The corresponding unadjusted changes will also be reported as a secondary analysis. Since this is a randomized trial, we expected the primary propensity adjusted and unadjusted results to be similar.

**Aim 1. TR+UC is superior to UC alone:** A 6-week program of TR targeting arm movement added to UC will result in better arm function as compared to UC alone. The primary endpoint is the change in ARAT score from baseline to 1 month after end of therapy (Visit 4).

The mean differences in ARAT score change from Visit 1 (baseline) to Visit 4 (1 month after end of therapy) will be compared on the log scale using an inverse propensity adjusted t test. A similar method will be used for the secondary change from Visit 1 to Visit 3 (end of therapy). We will first compare the combined TR + UC groups versus the UC group (Aim 1) and then compare TR+Sinemet+UC versus TR+placebo+UC under this model. (Aim 2). As a secondary analysis, we will report the corresponding unadjusted results.

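### The study statistician holds the pill code while Aim 2 analysis choices are still open, and the PI's emergency code is not stated to be per patient

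*Combined protocol and SAP*

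**What the plan says.** The Blinding section of the combined protocol and SAP gives the pill code to one role: "The sole person unblinded to pill type (for patients randomized to either TR+Sinemet or TR+placebo) will be the study statistician". The PI, the assessors, the treating therapists and all other staff are to stay blind to the pill.

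For emergencies, "With regard to the pill to which a TR patient was assigned, the study PI will be able to break the blind at any time". To make this possible, "a password-protected file and a hard copy sealed envelope will both be in the PI's possession", and these "will remain unopened unless an emergency unblinding event arises". What the file and the envelope contain is not described, and no log of openings is mentioned.

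Under Dispense Study Medication, "The UCLA Pharmacy will generate the two types of study pills". The two pills are made to look alike and are packed in blister packs of 18.

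The Statistical Analysis section says: "For all analyses, data not normally distributed will be appropriately transformed". The intention-to-treat population is described as "consisting of all randomized subjects and multiple imputation for missing data", with no imputation model. Two consecutive sentences place inverse-propensity weighting first among the secondary analyses and then at the base of the primary ones. The Aim 1 text names a weighted t test on the log scale and, in its next paragraph, an ANCOVA on baseline ARAT and propensity score. The Aim 2 text applies all of this again to Sinemet against placebo.

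**The concern.** Sinemet against placebo is the only double-blind comparison in the trial; TR against usual care is blind for assessors only. Its credibility depends on keeping knowledge of the pill away from anyone who shapes the data or the analysis.

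The plan gives that knowledge to the role most closely tied to the analysis and does not fix the analysis beforehand. A positive Aim 2 result could then be questioned on the ground that the method was settled by someone who could see which arm it favoured. The sponsor would have no documented step to answer with.

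The emergency arrangement raises a smaller, separate question. The PI is meant to stay blind, and a code held in one piece cannot be opened for one patient without showing the others.

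**Working it through.** **1. The plan's own figure.** Sample Size gives 80% power for Aim 1 with 54 TR and 18 UC patients, a difference of 5.7, SD 7.4 and two-sided alpha 0.05.

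- SE = 7.4 × √(1/54 + 1/18) = 7.4 × 0.2722 = 2.014
- 5.7 / 2.014 = 2.830, and 2.830 − 1.960 = 0.870
- Power = Φ(0.870) = 80.8% (79.7% with the noncentral t)

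The figure reproduces, and this point changes none of its inputs. It does confirm the number of coded patients: 27 + 27 = 54.

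**2. Is there a task that needs the code?** The public text describes no interim analysis, no monitoring board and no sample-size re-estimation by arm. Nor does it name a second, blinded analyst, a dummy-coded dataset or a date by which choices are frozen. No reason is given for unblinding the statistician during the trial.

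**3. What is settled for Aim 2, and what is open.**

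| Item | Settled | Open |
|---|---|---|
| Scale | Log scale for the ARAT t test | How zero scores or changes enter a log; the scale of the ANCOVA; which other endpoints are transformed, and how |
| Missing data | Multiple imputation | The imputation model |
| Role of weighting | Covariates of the propensity model | Primary or secondary |
| Test | Two methods named | Which one decides |
| Per-Protocol set | Numeric rule | Nothing material here |

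Zero scores can occur: inclusion requires an ARAT below 32, sets no lower limit, and accepts a visible flicker of movement.

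**4. How much room the choice of test leaves.** This is an illustration under assumed inputs, not a forecast: 27 against 27, no drug effect, baseline ARAT about 15 (SD 9), change SD about 7.4, correlation of change with baseline −0.3 or −0.6, log scale taken as change in log(ARAT + 1), 10,000 simulations per setting. Used alone, the log-scale weighted t test rejects in 4.2% and 4.7% of trials, and the raw-scale ANCOVA in 5.0% and 4.7%. Taking whichever gives the smaller p-value rejects in 8.0% and 8.8%.

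This measures the lack of a fixed method. It does not measure the effect of knowing the pill, because a two-sided p-value is the same whichever arm is called X. It does bear on the form of the remedy: X/Y labels alone would not remove this latitude. Settling the choices on data pooled over the pill arms would, because no between-pill comparison can then be seen.

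**5. The emergency code.** The right to break the blind is worded for one patient. The device is worded in the singular, with contents unstated. If it is one list, an opening made for 1 patient shows up to 54. With an assumed emergency risk q per patient, the chance of at least one opening is 1 − (1 − q)^54:

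| q | 0.5% | 1% | 2% | 5% |
|---|---|---|---|---|
| Chance | 24% | 42% | 66% | 94% |

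The documents give no value for q. Each blister pack holds only 18 pills, so the period at risk is short and the lower values are the more plausible ones.

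**The case against.** **Who makes the choices is not stated.** A reader might infer that the statistician makes data-dependent choices with the code in view. No sentence says so. The section on recruitment and enrollment has personnel of a referral hospital assisting with data analysis, and the Blinding section keeps all other personnel blind. This stands: the supportable statement is that the choices are unprotected, not that they are unblinded.

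**The latitude is narrower than it first looks.** The ARAT t test is already put on the log scale, the propensity covariates are listed, and the Per-Protocol set has a numeric rule. The restricted cubic splines belong to exploratory and Aim 3 analyses, so they do not count here. All of this stands. The open items in the table remain.

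**These are specification gaps whoever holds the code.** This is true, and step 4 shows it. But unsettled choices are easier to defend when the person settling them cannot see the arms, so the two faults compound each other.

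**The PI's code may already be per patient.** A reader might infer from the singular wording that any opening unblinds every patient, or that the file also holds assignments not yet made. Neither is stated. The right is worded for one patient, randomization is web-based, and nothing says that a list is prepared in advance. The first inference survives only as a condition; the second has no support. The PI is not named as an assessor or analyst, and the PI's discretion over MRI timing touches an Aim 3 biomarker, so any route to Aim 2 bias is indirect.

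**The word sole overlooks the pharmacy.** The pills look identical, so someone in the supply chain must hold a key. On its own this is a wording slip and biases nothing.

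**The study is powered for Aim 1 only.** This is so, and it limits the weight of the point. Aim 2 is still a stated aim with its own superiority claim.

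**Conclusion.** The point holds in a limited form. The plan gives the pill code to the study statistician without a stated need. It leaves several Aim 2 choices open and has no step that keeps the two apart. Nothing in the documents shows that any choice will be made with knowledge of the pill, and the size of any resulting bias cannot be derived from them.

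The PI's emergency code is a conditional risk: up to 54 patients at the planned size if it is a single list, and only the patient concerned if it is not.

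This is a cheap improvement to the only double-blind comparison, not a defect that invalidates the design. Aim 1 is unaffected, because the pill code plays no part in TR against usual care. The conclusion assumes that no unblinded task or separate blinded analyst is described in text outside the public documents.

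**What to change.** Amend the Blinding section, with a cross-reference from Statistical Analysis.

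(a) **Custody and sign-off.** The pharmacy, which already prepares both pills, holds the pill code and is named as holder in place of the statistician. The statistician settles and signs off three things on data pooled across the two TR pill arms: the transformations (including the handling of zeros on the log scale), the imputation model, and the primary method (weighted t test or ANCOVA, and the role of the weighting). The Aim 2 analysis is then run under X/Y labels, which is all that the propensity and imputation models need. The true code is released only after the data are locked.

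(b) **Emergency codes.** State that there is one code-break per patient, issued after that patient is randomized, and that each opening is logged. The PI's right to unblind in an emergency is unchanged.

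The cost is protocol wording, a change of code custodian and one documented sign-off. Sample size, visits and treatment do not change. The documents do not describe the pharmacy's capacity, so the sponsor should confirm that it can take on custody.
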